12.8 Hematologic Improvement (HI)

Improvements must last at least 2 months in the absence of ongoing cytotoxic therapy. When protocol therapy requires the initiation of further treatment before the 2 month period, patients can be included in the response criteria into which they fit at the time therapy is started.

Hematologic improvement should be described by the number of individual, positively affected cell lines (eg, HI-E; HI-E + HI-N; HI-E + HI-P + HI-N).

1. Erythroid response (HI-E)

For patients with pretreatment hemoglobin less than 11g/dL: greater than 1.5 g/dL increase in hemoglobin, relevant reduction of units of RBC transfusions by an absolute number of at least 4 RBC/8wk compared with the pretreatment transfusion number in the previous 8 wk. (*)

(*) Only RBC transfusions given for Hgb > 9.0 g/dL pretreatment will count in the RBC transfusion response evaluation.

2. Platelet response (HI-P)

Memorial Sloan Kettering Cancer Center
[name]
[name]

For patients with a pretreatment platelet count less than 100 000/mm³: an absolute increase of 30 000/mm³ or more for patients starting with more than 20 000/mm³ platelets, an increase from less than 20 000/mm³ to greater than 20 000/mm³, and by at least 100%.

3. Neutrophil response (HI-N)

For patients with pretreatment neutrophil count less than 1 000/mm³: at least a 100% increase and an absolute increase of more than 500mm³.

4. Progression/relapse after HI

One or more of the following: A 50% or greater decrement from maximum response levels in granulocytes or platelets, a reduction in hemoglobin concentration by at least 1.5 g/dL, or transfusion dependence (in the absence of other explanation, such as hemolysis, hemorrhage, etc).

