2.0 OBJECTIVES AND SCIENTIFIC AIMS

Primary Endpoint:

Phase I: Define the hematologic and non-hematologic toxicities of combining a hypomethylating agent (Decitabine, DAC) with escalating doses of the transcriptional modifying agent tretinoin (All Trans Retinoic Acid), and define the MTD of tretinoin in combination with decitabine.

Phase II: Determine the clinical remission rate (rate of Complete Remission, Partial Remission) of the combination of decitabine and tretinoin in patients with myelodysplastic syndromes, and determine the rate of Hematologic Improvement.

Secondary Endpoints (Phase I and Phase II):

1. Evaluate the ability of decitabine and tretinoin to affect bone marrow function by monitoring frequency of transfusions, frequency of bleeding and infection, and changes in bone marrow morphology and cytogenetics.
2. Evaluate differentiation (using morphology and flow cytometry) and apoptosis (using flow cytometry) induced by treatment with decitabine and tretinoin.
3. Perform gene profiling studies to determine if gene expression changes are induced by decitabine and tretinoin.
4. Evaluate the ability of decitabine and tretinoin to cause demethylation of specific genes.
5. Correlate clinical response with gene expression, demethylation of specific genes, and flow cytometric indicators of differentiation and apoptosis.

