12.1 CRITERIA FOR THERAPEUTIC RESPONSE/OUTCOME ASSESSMENT

Response will be determined by the MDS International Working Group criteria (47).

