Additionally, secondary objectives will be examined in patients enrolled into phase I and phase II components of the trial. The proportion of Hematologic Improvements will be recorded. The frequency of transfusions, bleeding and infections will be summarized. Peripheral blood and bone marrow aspirate mononuclear cells will be assessed for the extent of DNA methylation using PCR based technologies. The expression and methylation status of specific genes will be analyzed, focusing on, but not necessarily restricted to the following genes: p57, p 21, p73, p15INK4b, TGF β RII, RAR β , and JunB. In this study we will examine whether methylation of these genes (yes/no) as well as flow cytometric indicators of differentiation and apoptosis, correlate with response to treatment. Associations will be examined using a Fishers exact test. These analyses are exploratory and hypothesis-generating.

In addition, bone marrow and blood mononuclear cells will be analyzed using gene profiling (Affymetrix). In order to attempt to identify genes that are most affected by treatment, a paired sample t-test will be used to rank the genes. Samples pre and post chemotherapy will be paired together and a fold change will be computed for each pair. The log of the fold change will then be used and genes will be scored by how large and consistent the fold change is among the patients. To deal with issues of non-normality of the signal levels p-values will be computed using a permutation algorithm which shuffles the sample labels and recomputes the t-score. To correct for multiple testing the False Discovery Rate (FDR) method will be used to compute rate of false positives. Due to the two-stage design, and uncertainty regarding the rate of disease response, the exact number of samples that will be included in the microarray analysis is unknown.

Frequencies of toxicities based on the NCI Common Toxicity Criteria version 2.0 will be tabulated.

A minimum of 27 patients (including 6 patients from the phase I component) and a maximum of 40 patients will be accrued to the phase II component of this trial. Approximately 3-4 patients will be accrued per month, and hence, the trial will be completed in approximately 2 years.

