20.1 APPENDICES

Appendix I: The International Prognostic Scoring System (2)

BM Blast %	<5%	0.0
	5-10%	0.5
	11-20%	1.5
	21-30%	2.0
Cytogenetics	Good Risk [-Y, del(5q),del(20q), normal]	0.0
	Intermediate Risk [8+, other]	0.5
	Poor Risk [Ch 7 abn., \geq 3 abnormalities]	1.0
Cytopenias	0-1 cytopenia	0.0
	2-3 cytopenias	0.5

Memorial Sloan Kettering Cancer Center
[name]
[name]

Cytopenias: ANC < 1.5, HGB < 10.0, PLT < 100,000

Calculating the IPSS Score and determining the IPSS risk category:

Using the table above, total the scores obtained for the three individual categories (i.e., cytopenias, cytogenetics and bone marrow blast count).

Depending on the total score, the patient is determined to have IPSS Low, Intermediate-1, Intermediate-2, or High risk MDS.

Total IPSS score of 0 = Low Risk

Total IPSS score of 0.5-1.0 = Intermediate-1 Risk

Total IPSS score of 1.5-2.0 = Intermediate-2 Risk

Total IPSS score of ≥ 2.5 = High Risk

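### As printed, the 12.8 HI-E footnote ignores red-cell units given at hemoglobin 9.0 g/dL or below, so a patient who stops needing such transfusions cannot meet the transfusion limb

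*Combined protocol and SAP*

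**What the plan says.** Section 12.8 defines HI-E for a stated group: "For patients with pretreatment hemoglobin less than 11g/dL". It then lists two routes with no conjunction between them: "greater than 1.5 g/dL increase in hemoglobin, relevant reduction of units of RBC transfusions by an absolute number of at least 4 RBC/8wk". The transfusion reduction is measured against the 8 weeks before treatment. A footnote to that limb restricts which units count: "Only RBC transfusions given for Hgb > 9.0 g/dL pretreatment will count in the RBC transfusion response evaluation". No other section restates, explains or corrects the 9.0 cut-off. Section 12.1 says that response follows the International Working Group criteria (reference 47), but the HI-E transfusion rule appears only in 12.8.

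HI is used in three places that matter here:

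- Section 2.0 lists it in the phase II primary endpoint statement: "and determine the rate of Hematologic Improvement".
- Section 14.1 places it among the secondary analyses: "The proportion of Hematologic Improvements will be recorded". The population is given as "secondary objectives will be examined in patients enrolled into phase I and phase II components of the trial".
- Section 9.0 lets patients with HI, or a marrow PR or CR, by the end of cycle 6 go on to as many as 10 cycles. It removes those whose best response is stable disease.

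**The concern.** The transfusion limb is there to recognise a patient whose need for red cells has fallen. Units given at a low hemoglobin are the clearest evidence of need. The printed footnote discards exactly those units and keeps the ones given at higher values. A patient with heavy baseline use at low hemoglobin who becomes transfusion-free gets no credit on this limb, while a patient with lighter use at higher hemoglobin gets full credit.

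At stake are the HI rate that the trial reports and, for an individual patient, possibly whether treatment continues beyond cycle 6.

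**Working it through.** The plan gives no figure for this limb to reproduce, so the check applies the printed rule to simple transfusion histories.

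**Inputs (12.8).** The limb is met if the counted fall is at least 4 units per 8 weeks. A unit counts only if given for hemoglobin above 9.0 g/dL.

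**Formula.** Counted fall = baseline units meeting the footnote − on-study units. Every hypothetical patient below becomes transfusion-free, so on-study units are 0. The result then does not depend on whether the footnote also filters on-study units.

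| Baseline units in 8 weeks | Fall in all units | Counted fall as printed (> 9.0) | Counted fall if sign reversed (≤ 9.0) |
|---|---|---|---|
| A: 8, all at 8.0 g/dL | 8 | 0 − 0 = 0, not met | 8 − 0 = 8, met |
| B: 4, all at 9.5 g/dL | 4 | 4 − 0 = 4, met | 0 − 0 = 0, not met |
| C: 4 at ≤ 9.0 and 2 at > 9.0 | 6 | 2 − 0 = 2, not met | 4 − 0 = 4, met |

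Any patient with fewer than 4 baseline units given above 9.0 cannot meet the printed limb. With fewer than 4 baseline units in total, neither version can be met, so the sign makes no difference.

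**Alternative reading of the footnote.** The word "pretreatment" might describe the patient and not each unit. Patients with pretreatment hemoglobin of 9.0 or below would then lose the limb altogether. Either way the more anemic patients are excluded.

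**When a mis-score reaches overall HI.** Take the two HI-E limbs as alternatives. The footnote changes HI-E only for a patient without a hemoglobin rise above 1.5 g/dL. It changes overall HI only if that patient also has no HI-P and no HI-N.

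**Weight of one patient.** Section 14.1 examines secondary objectives in both phases, so N is the combined enrollment.

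- Largest N: 18 (phase I maximum) + 40 (phase II maximum) − 6 (carried over) = 52.
- Smallest N, given that stage 1 is completed: 27 already includes the six MTD patients, so add the fewest possible phase I patients at other doses. An MTD of 85 mg/m²/day requires at least 3 + 3 = 6 at 45 and 65. Any other MTD requires at least 2 patients with DLT at another level. The minimum is 27 + 2 = 29.
- If stage 2 is completed, the smallest N is 40 + 2 = 42.

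One patient is worth 100/52 = 1.9, 100/42 = 2.4 or 100/29 = 3.4 percentage points.

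**Check on the efficacy rule.** Section 14.1 counts CR or PR only. P(positive) = Σ over x = 3 to 27 of P(X₁ = x) × P(X₂ ≥ 7 − x), with X₁ ~ Bin(27, p) and X₂ ~ Bin(13, p). This gives 0.0977 at p = 0.10 and 0.9001 at p = 0.25, in line with the stated error rates of 0.10 and 0.10. HI-E is not an input. The CR and PR definitions in 12.2 and 12.3 do not use the footnote.

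**The case against.** The strongest reply is that everything turns on one character. The text was extracted from a PDF, and some symbols came through as markup (the creatinine limit in 6.2, the blood-count limits in 12.2), so a reading error cannot be ruled out. Section 12.1 also names outside criteria as governing, and a scorer who went to them might never apply the printed footnote. Both points stand as reasons to verify before editing. Neither removes the defect in the printed rule, which nothing else in the documents corrects.

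Impact is also limited, and this stands in full. Section 14.1 gives HI no threshold and no test. Transfusion frequency is summarised separately without the footnote, so a transfusion benefit would still be visible. Continuation under 9.0 is permissive, and 13.2, which removes patients without at least a PR after 6 cycles, already conflicts with it.

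Several stronger readings are tempting but unsupported:

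- **That the documents prove the sign is reversed.** They print no other version. The reversal is inferred from the purpose of the limb.
- **That the HI rate is biased by some stated amount or in a known direction.** The documents give no distribution of pre-transfusion hemoglobin or unit counts. Errors can run both ways, as patients A and B show.
- **That only a narrow hemoglobin band can count**, from 9.0 up to the HI-E limit of 11 or the Appendix I anemia limit of 10.0. Neither limit governs when blood is transfused.
- **That a patient whose total use is unchanged would be credited.** This needs the footnote to filter on-study units as well, which its wording does not establish.
- **That one patient is worth 1/27 of the HI rate.** Section 14.1 uses both phases, so the denominator is at least 29 once stage 1 is complete.

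**Conclusion.** The point holds for the text as printed. The footnote makes the transfusion limb unattainable for a patient whose baseline units were all given at 9.0 g/dL or below, and attainable for one with 4 units given above 9.0. It is a rule that gives a wrong result, not a missing detail, and it should be corrected.

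The number of patients affected and the net direction cannot be computed. Each patient whose status changes moves the reported rate by about 1.9 to 3.4 points. This assumes that all patients enrolled in both phases form the denominator, that phase II completes at least stage 1, and that the two HI-E limbs are alternatives. A reader might infer that the trial's efficacy conclusion is at risk. It is not: the two-stage CR/PR rule, sample size, alpha and power do not depend on HI-E.

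**What to change.** 1. Check the sign in the 12.8 footnote in the source PDF, and check the rule against the working group criteria cited in 12.1.
2. If the printed sign is confirmed and the cited criteria agree with the inference, change the footnote so that red-cell units given for hemoglobin of 9.0 g/dL or below are the ones that count.
3. Write "or" between the hemoglobin-rise limb and the transfusion-reduction limb.
4. Re-score HI-E, and overall HI where it depends on HI-E, for any patient already assessed on the transfusion limb, where pre-transfusion hemoglobin is on record.

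The cost is one sign, one word and two look-ups. Either direction of the sign needs the same pre-transfusion hemoglobin, so the correction adds no visit, procedure or data item to what the rule already requires. Re-scoring may be incomplete: 8.2, 8.3 and Appendix IV call for transfusion requirements but do not say that the hemoglobin at each transfusion is recorded.

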13.0 CRITERIA FOR REMOVAL FROM STUDY

- 13.1 Progressive disease and transformation to acute leukemia (Response criteria are defined in section 12.0)
- 13.2 Failure to achieve at least a PR after 6 cycles of treatment
- 13.3 Unacceptable toxicity defined as grade III or IV non-hematologic toxicity requiring greater than 8 weeks to return to < grade 2 (NCI CTC version 2.0).
- 13.4 Patient's withdrawal of consent for any reason
- 13.5 Patient non-compliance with the treatment and monitoring plan
- 13.6 Patient death

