Treatment will be recycled every 4 weeks, provided there is adequate recovery from non-hematologic toxicities. The effects of decitabine and escalating doses of tretinoiin on markers of differentiation and apoptosis, and on expression of key genes will be assessed.

FIGURE 1.1: Study Design

Memorial Sloan Kettering Cancer Center
[name]
[name]

	Treatment Period →								
	Cycle # 1 →				Cycle #2, #3, #4, etc. →				End of Study
Decitabine	X				X				
Tretinoin			X				X		
Treatment Days (D)	D1 - D5	D 6 - D 9	D10 - D19	D 20 - D 28	D 1 - D 5	D 6 - D 9	D 10 - D 19	D 20 - D 28	Day X

Patients will receive treatment for a minimum of 4 cycles, barring removal for progression of disease or excessive toxicity. Patients must achieve hematologic improvement (HI) or Bone Marrow PR/CR by the completion of cycle #6. Patients achieving HI or bone marrow PR/CR by the completion of cycle #6 may receive up to a total of 10 cycles of therapy, barring excessive toxicity. If the best response after cycle #6 is Stable Disease, these patients will be removed from study. Patients in the phase I study will continue at the study entry dose. Treatment will be interrupted for grade III or IV non-hematologic toxicity attributable to tretinoin or decitabine. Therapy may be resumed with the next cycle of treatment as long as the toxicity has decreased to < grade 2 within 8 weeks of the last treatment administration. However, these patients will receive a 25% dose reduction in tretinoin or decitabine (which ever treatment is suspected or both if the attribution is unknown) when treatment resumes. All patients will be followed for Serious Adverse Events (SAEs) for 30 days after the completion of the last cycle of therapy (each cycle is 4 weeks).

TIME TO COMPLETION: It is anticipated the study will complete accrual in 18–24 months.

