Once the MTD is established, patients will be accrued to the phase II portion of the study which will evaluate the efficacy of decitabine in combination with the MTD of tretinoin. The phase II study will have a 2-stage design. In the first stage of this design, twenty seven patients will be treated. Patients treated at the tretinoin MTD (6 patients) in the phase I portion of the study will be carried over and counted among the patients in stage 1. If two or fewer responses (CR or PR) are seen among the first 27 patients, the study will be closed for lack of efficacy. If at least three responses (CR or PR) are seen in the first stage, then an additional 13 patients will be accrued in the second stage. To qualify as a non-responder, patients must undergo disease re-evaluation studies (bone marrow and complete blood counts) after completing four cycles of therapy.

Treatment will be recycled every 28 days, provided there is adequate recovery from non-hematologic toxicities. The start of cycle #1, or subsequent cycles may be delayed for up to 2 weeks in the event of 1) uncontrolled infection, or 2) other abnormalities that would preclude patient eligibility (see sections 6.1 and 6.2).

Patients will receive treatment for a minimum of 4 cycles, barring removal for progression of disease or excessive toxicity. Patients must achieve hematologic improvement (HI) or Bone Marrow PR/CR by the completion of cycle #6. Patients achieving HI or bone marrow PR/CR by the completion of cycle #6 may receive up to a total of 10 cycles of therapy, barring excessive toxicity. If the best response after cycle #6 is Stable Disease, these patients will be removed from study. Patients in the phase I study will continue at the study entry dose. Treatment will be interrupted for grade III or IV non-hematologic toxicity attributable to tretinoin or decitabine. Therapy may be resumed with the next cycle of treatment as long as the toxicity has decreased to < grade 2 within 8 weeks of the last treatment administration. However, these patients will receive a 25% dose reduction in tretinoin or decitabine (which ever treatment is suspected or both if the attribution is unknown) when treatment resumes. All patients will be followed for Serious Adverse Events (SAEs) for 30 days after completion of the last cycle of therapy (each cycle is 28 days).

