12.2 Complete Remission (CR)

Bone marrow evaluation: Repeat bone marrow showing 5% or less myeloblasts with

**Memorial Sloan Kettering Cancer Center
[name]
[name]**

normal maturation of all cell lines. Persistent dysplasia will be noted. (*)

Peripheral Blood: Absolute values must last at least 1 months. In some circumstances, protocol therapy may require the initiation of further treatment before the 1 month period. Such patients can be included in the response criteria into which they fit at the time therapy is started. Transient cytopenias during repeated chemotherapy courses should not be considered as interrupting durability of response, as long as they recover to the improved counts of the previous course.

Hgb \geq 11 g/dL (untransfused, patient not on erythropoietin)
Neutrophils \geq 1500/mm³ or more (not on myeloid growth factor)
Platelets \geq 100,000/mm³ or more (not on thrombopoietic factor)
Blasts 0%

(*) Dysplastic changes should consider the normal range of dysplastic changes (modification).

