12.3 Partial Remission (PR)

Absolute values must last at least 1 months unless interrupted by therapy as described above.

All the CR criteria (if abnormal before treatment) except:

Bone marrow evaluation: Blasts decreased by 50% or more over pretreatment, but still more than 5 %. Cellularity and morphology are not relevant

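### Section 13.2 takes off study any patient below PR after six cycles, while Sections 1.0 and 9.0 let patients with HI alone continue to ten cycles

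*Combined protocol and SAP*

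**What the plan says.** Three places in the protocol decide what happens after cycle 6.

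- **Section 13.2** (removal criteria): "Failure to achieve at least a PR after 6 cycles of treatment". No exception is given for HI or marrow CR.
- **Section 1.0** (summary): "Patients must achieve hematologic improvement (HI) or Bone Marrow PR/CR by the completion of cycle #6".
- **Section 9.0** (treatment plan) repeats that requirement and adds "Patients achieving HI or bone marrow PR/CR by the completion of cycle #6 may receive up to a total of 10 cycles of therapy", unless toxicity prevents it. It then says "If the best response after cycle #6 is Stable Disease, these patients will be removed from study".

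The response definitions are in Section 12. PR (12.3) requires "All the CR criteria (if abnormal before treatment) except" for the marrow item. The CR list in 12.2 that it refers to includes a platelet count of "100,000/mm³ or more (not on thrombopoietic factor"). HI (12.8) is scored separately for each cell line and has no marrow requirement. For platelets it asks for "an absolute increase of 30 000/mm³ or more for patients starting with more than 20 000/mm³ platelets". Marrow CR, also numbered 12.3, is a further category and does not need the CR blood counts. Section 12.4 defines Stable Disease as falling short of PR without progression for at least 2 months.

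**The concern.** The protocol sets two different bars at the same time point. Under 1.0 and 9.0, HI by the end of cycle 6 is sufficient to continue. Under 13.2, anything less than PR ends participation. If 13.2 governs, the HI alternative in 1.0 and 9.0 has no effect.

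This rule has to be applied to individual patients. Cycle 7 for a patient with HI only is permitted by 9.0 and is a deviation under 13.2, and Section 16.2 plans compliance audits at least twice a year. Following 13.2 instead withdraws treatment from a patient who has a protocol-defined benefit. Section 2.0 names the HI rate among the phase II aims, so these patients matter to the trial.

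**Working it through.** **Step 1. Can a patient have HI without PR?** The inputs are the platelet thresholds in 12.2, 12.3 and 12.8.

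- Start 45,000/mm³, on treatment 80,000/mm³.
- HI-P: 80,000 − 45,000 = 35,000 ≥ 30,000, from a start above 20,000. Met, provided it meets the 2-month duration rule in 12.8 or its allowance for earlier retreatment.
- PR: platelets were abnormal at baseline (45,000 < 100,000), so the CR threshold carries over. 80,000 < 100,000. Not met, whatever the marrow shows.

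In general, a rise of exactly 30,000 from any start above 20,000 and below 70,000 stays under 100,000.

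The punctuation of 12.8 leaves some doubt whether the requirement for a 100% increase applies only to patients starting below 20,000. The result does not depend on this. A rise from 45,000 to 95,000 is +50,000 and 50/45 = +111%, which is HI-P on either reading and still below 100,000. Neutrophils give the same picture: 400 to 1,000/mm³ is +600 and +150%, which is HI-N, but 1,000 is below the 1,500 needed for PR.

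**Step 2. Apply each rule to this patient after cycle 6.**

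| Rule | Outcome for HI without PR |
|---|---|
| 1.0 and 9.0, HI or bone marrow PR/CR | May continue, up to cycle 10 |
| 13.2, at least PR | Removed |
| 9.0 Stable Disease sentence, with 12.4 read literally | Removed, because 12.4 does not exclude HI |

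The third row shows that 9.0 read with 12.4 can also point both ways. In context 9.0 plainly contrasts Stable Disease with HI, but 12.4 does not say so.

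**Step 3. Does other text settle it?** No section ranks the others. The cycle-4 sentence in 9.0, beginning "To qualify as a non-responder, patients must undergo disease re-evaluation studies", concerns who counts as a non-responder and does not address continuation after cycle 6.

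**Step 4. Difference per affected patient**, as maxima without delays or dose reductions. Inputs: 100 mg/m² decitabine and 10 tretinoin days per 28-day cycle (9.0), marrows after even-numbered cycles (10.3), adverse-event follow-up to 30 days after the last cycle (11.4).

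| Quantity | Stop at 6 | Up to 10 |
|---|---|---|
| Decitabine | 6 × 100 = 600 mg/m² | 10 × 100 = 1,000 mg/m² |
| Tretinoin days | 6 × 10 = 60 | 10 × 10 = 100 |
| Tretinoin at 45 mg/m²/day | 60 × 45 = 2,700 mg/m² | 100 × 45 = 4,500 mg/m² |
| Tretinoin at 85 mg/m²/day | 60 × 85 = 5,100 mg/m² | 100 × 85 = 8,500 mg/m² |
| On-treatment disease-assessment marrows | 3 (after 2, 4, 6) | 5 (after 2, 4, 6, 8, 10) |
| Adverse-event follow-up ends | 6 × 28 + 30 = day 198 | 10 × 28 + 30 = day 310 |

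Extra treatment time: 4 × 28 = 112 days = 16 weeks. If the dose were de-escalated to 15 mg/m²/day, tretinoin would be 60 × 15 = 900 versus 100 × 15 = 1,500 mg/m².

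**Step 5. Phase II design.** The exact two-stage calculation (stop if 2 or fewer of 27 respond; positive if 7 or more of 40 respond) gives a probability of a positive result of 0.0977 at a 10% response rate and 0.9001 at 25%. Both agree with Section 14.1, and neither depends on the cycle-6 rule.

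**The case against.** The strongest counter-argument is about which text is at fault. Section 1.0 is a summary that repeats 9.0 almost verbatim, so the two are not independent evidence of intent. Section 13.2 also agrees with the Stable Disease sentence in 9.0 if 12.4 is read literally. On that view PR could be the intended bar, and the HI wording could be the error. This stands as far as intent goes: the text alone does not prove which rule was meant. It does not remove the conflict, because 9.0 states expressly that HI satisfies the cycle-6 requirement.

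Nor does the permissive wording (patients *may* receive further cycles) reconcile the sections, because the sentence before it makes HI sufficient. Reading 13.2 as ending only study follow-up also fails: 9.0 and Section 13 both speak of removal from study.

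Two limits are fair. The conflict extends to patients with marrow CR only if *bone marrow PR/CR* means a marrow-level response. That is the natural reading, but the protocol does not define bone marrow PR, so only the HI case is firm. The exposure figures simply spell out 6 versus 10 cycles and are not an estimated effect on the trial.

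**Conclusion.** Section 13.2 contradicts Sections 1.0 and 9.0 for any patient with HI but not PR after cycle 6, and the protocol's own definitions allow such patients. The consequence is up to 4 cycles of treatment per affected patient, with the marrows and follow-up that go with them. How many patients would be affected, and whether any would reach CR or PR in cycles 7 to 10, cannot be derived from the documents, so no effect on the primary response count is claimed. That 13.2 is the slip is a judgement: the treatment plan sets out the HI rule explicitly and the summary repeats it. The contradiction itself does not depend on that judgement. It should be corrected, as an inconsistency in an operative stopping rule and not as a flaw in the statistical design.

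**What to change.** If HI is the intended bar:

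- Reword 13.2 so that the ground for removal is *neither HI nor a bone marrow PR/CR reached by the end of cycle 6*.
- State in 12.4 that, for the cycle-6 decision, Stable Disease excludes HI and marrow CR. If the published response definition is to be left intact, the same clause can sit beside the removal sentence in 9.0 and its copy in 1.0.
- Say in a few words what *bone marrow PR/CR* means, since the corrected 13.2 would rely on it.

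If PR is the intended bar, leave 13.2 and change the cycle-6 sentences in 1.0 and 9.0 to match.

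The cost is a line or two of text. Sample size, two-stage boundaries, the timing of the stage 1 decision and the assessment schedule stay as they are, and Section 14 needs no edit. Under the HI rule, the further cycles, marrows and follow-up are those that 1.0 and 9.0 already provide for.
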